 Onset of pain relief as determined by the time to meaningful relief 	Time to first use of rescue medication		
 Overall relief from pain based on measures of pain intensity and pain relief 	The cumulative proportion of participants taking rescue medication over the 24 hour period.		
O Global assessment of the investigational product To assess the safety and tolerability of the investigational product in terms of adverse events (AEs) and clinical parameters	Time to first perceptible relief measured by a stopwatch, time to meaningful relief measured by a stopwatch, and time to first perceptible relief confirmed by meaningful relief defined as the time to perceptible pain relief (the first stopwatch time) for those participants who had meaningful pain relief (the second stopwatch time)		
	• Pain Intensity Difference (PID) and Pain Relief scores at 0.5, 1, 1.5, 2, 3, 4, 5, 6, 7, 8, 9, 10, 11, 12, 14, (16, 18, 20 if awake), 22 and 24 hours post-dose		
	Peak PID and peak pain relief		
	Cumulative percent of participants with 'at least a 2-point PID' over time		
	Global assessment of the investigational product		
	Collect AE and clinical paramaeters		

Overall Design:

This is a single center, randomized, double-blind, parallel, placebo-controlled study in participants experiencing moderate to severe postoperative dental pain. The study will consist

Version 4.0 / 13 Mar 2023

Page 14 of 67

of a Prescreening telephone call, a Screening Visit, a one day Treatment Period and a Post-Operative phone call or visit. Eligible participants who have undergone surgical extraction of three or four third molars, two of which must be mandibular partial or full bony impacted, will be randomized into one of five treatment groups and kept in-house and evaluated for efficacy and safety at the study site through completion of all trial procedures.

Disclosure Statement: This is a parallel group treatment study with 5 arms that is participant and investigator blinded.

Intervention Model: Parallel Primary Purpose: Treatment

Number of Arms: 5
Masking: No masking
Number of Participants:

Approximately 750 participants will be screened to achieve 540 randomly assigned to study intervention and 528 evaluable participants for an estimated total of 144 evaluable participants per active intervention group with 48 participants in the caffeine 100 mg arm and 48 participants for placebo (total of 5 groups).

Intervention Groups and Duration:

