4.2 Scientific Rationale for Study Design

The study is designed specifically to measure the analgesic effectiveness and capture side effect profiles of naproxen sodium and caffeine FDC compared to the individual active ingredients on acute post-surgical dental pain in healthy participants who could benefit from the administration of an analgesic medication. The molar impaction dental pain model has been widely employed with OTC and prescription pain medications, since it is easily standardized, and the participants are relatively healthy and homogeneous. In addition, there are extensive data substantiating the usefulness of the dental pain model in predicting the relative efficacy of a wide range of analgesic medications by comparing several measures of analgesic efficacy, including onset, peak effect, and duration of analgesic activity (Cooper, 2010, Cooper 1976, Kleinert, 2008).

Time to onset will be measured using a double stopwatch method. The double-stopwatch method for measuring first perceptible relief and meaningful relief was developed using the dental pain model (Desjardins 2002). After ingesting the study medication, the participant is asked to depress a stopwatch button when first perceiving any relief (First Perceptible Relief). If and when this stopwatch is depressed, the participant is then given a second stopwatch and asked to depress the button when the relief is perceived as meaningful (Meaningful Relief). Using this method, onset to First Perceptible and Meaningful Relief can be quantified to the nearest minute. This method has been proven to be sensitive and reliable for measuring analgesic onset (Cooper 2010).

The endpoints and study design are consistent with most recent Guidance by FDA and methods advocated by experts (Cooper 2016 and Singla 2014). Additionally, if a participant does not get sufficient pain relief, then rescue medication approved for treating acute pain (e.g., hydrocodone/acetaminophen) may be requested and will be provided under the supervision of the study site staff.

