6.5.1 Rescue Medicine

If adequate pain relief was not achieved, then participants are permitted to take rescue medication, although they will be encouraged to wait 2 hours to allow the investigational product time to take effect. The study site will supply the rescue medication that will be obtained locally. Rescue medication will be dispensed in a hierarchical method starting with ibuprofen 400 mg. Should the participant not experience adequate pain relief, Hydrocodone 5 mg/Acetaminophen 325 mg tablets or other appropriate analgesics (such as an additional ibuprofen dose) may be used at the discretion of the Investigator. Rescue medication is also available on return of pain and the time of rescue medication will be recorded in the source documents. Pain assessments will be performed immediately before the first dose of rescue medication.

- Rating of Pain Intensity (NRS);
- Rating of Pain Relief (Categorical);
- Global Assessment of investigational product as a pain reliever.

All active stopwatch elapsed time(s) will be stopped at the time of rescue administration and recorded on the case report form.

Participants will be queried in a nonspecific fashion for any adverse events. All observed and reported AEs will be collected and recorded on the case report form. The information recorded will be based on signs and symptoms reported by the participant or observed by the research coordinator during clinical evaluation.

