"Stop the stopwatch when you first begin to feel any pain-relieving effect whatsoever of the drug. That is, when you first feel a little relief. This does not necessarily mean that you feel completely better, although you might, but when you first feel any difference in the pain that you have now."

The participant will notify the Study Coordinator as soon as this stopwatch is stopped. The elapsed time on stopwatch A will be recorded in the case report form as the time to **first perceptible pain relief**. The participant will then be asked:

"Do you consider the relief you experienced meaningful?"

This answer will be recorded by the study coordinator in the case report form. If the participant answers "Yes" to this question, then meaningful pain relief is confirmed. The time recorded in the case report form for time to **meaningful pain relief confirmed will be the same time recorded as first perceptible pain relief.** The participant will not be given the second stopwatch. If the participant does not consider the relief to be meaningful, (by stating No), the participant will be given a second, covered stopwatch with instructions to:

"Stop this stopwatch when you have meaningful relief, that is, when the relief from the pain is meaningful to you."

The elapsed time on stopwatch B will be recorded in the case report form as time to **meaningful pain relief determined**. Unless meaningful pain relief is achieved, the participant will always have an active stopwatch in front of them.

If the participant never experiences first perceptible pain relief, they will retain stopwatch A for the entire 24-hour evaluation period. If the participant experiences first perceptible pain relief but not any meaningful pain relief (confirmed or determined), they will retain stopwatch B for the remainder of the 24-hour evaluation period.

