2.2 Study Design

This is a single center, randomized, double-blind, parallel, placebo-controlled study in participants experiencing moderate to severe postoperative dental pain. The study will consist of a Prescreening telephone call, a Screening Visit, a one day Treatment Period and a Post-Operative phone call or visit. Eligible participants who have undergone surgical extraction of three or four third molars, 2 of which were mandibular partial or full bony impacted third molars will be kept in-house and evaluated for efficacy and safety at the study site through completion of all trial procedures.

Qualified participants will then be randomized into one of five treatments. Approximately 750 participants will be screened prior to surgery. Approximately 540 will have surgery and approximately 528 will be randomized to a specific treatment. For an overview on the study design and study procedures, see figure 1 below:

-	Screening Phase		Treatm		Follow up Phase		
Trial Days	Day -28 to -1	Day 1 Pre-surgery	Day 1 Surgery	Day 1 Post-surgery	Day 1	Day 2	2-5 days after discharge
		Check-in to study site	Surgical teeth extraction	Categorical pain NRS pain	Stopwatch method NRS pain, Pain relief	Stopwatch method NRS pain Pain relief Global assessment	Phone call or visit

Figure 1 – Design Overview

★ = randomized study intervention of:

naproxen sodium/caffeine 220/65 mg; naproxen sodium/caffeine 2 x 220/65 mg; naproxen sodium 220 mg; caffeine 100 mg; or placebo.

Screening Phase

Eligible participants will be screened and selected up to 28 days prior to oral surgery and dosing with investigational product (study intervention).

Treatment Phase

Following selection, qualified participants will enter the Treatment Phase and be scheduled for their surgical teeth extractions. After completion of the surgical teeth extractions, participants will remain at the study site for observation. Participants with appropriate pain requirement will be randomized into one of five (5) treatment groups receiving study intervention. Participants will rate their pain severity and pain relief over the next 24 hours. Onset of analgesia will be measured using a two-stopwatch approach. The first stopwatch will be used to capture the time when any pain relief is first perceived. The second stopwatch will be used to capture the time when pain relief becomes meaningful to the participant. After completion of all trial procedures, participants will be discharged from the study site.

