Time to meaningful relief is the time when the Participant experiences relief that is meaningful after the administration of study drug and stops the second stopwatch. If it is not stopped, time will be censored at the time of last pain relief score assessment or at the first use of rescue medication, whichever comes first.

Time to first perceptible relief confirmed by meaningful relief:

Time to first perceptible relief confirmed by meaningful relief is defined as the time to perceptible pain relief (the first stopwatch time) for those Participants who had confirmed meaningful pain relief immediately after first stopwatch and it will be time to meaningful pain relief (the second stopwatch time) for those Participants who did not confirm the meaningful relief before second stopwatch. If stopwatch is not stopped, time will be censored at the time of last pain relief score assessment or at the first use of rescue medication, whichever comes first.

Time to the First Use of Rescue Medication:

Time to first use of rescue medication for pain is defined as the time from first study drug administration to the first use of rescue medication. If rescue medication for pain is not taken, the time will be censored at the time of the last pain intensity score assessment.

Time to achieve complete pain relief:

Time to achieve complete pain relief is defined as the time from first study drug administration to the achieve complete pain relief. If complete pain relief not achieved, the time will be censored at the time of the last pain relief score assessment.

Cumulative proportion of Participants taking rescue medication:

The cumulative proportion of Participants taking rescue medication will be calculated as the cumulative number of Participants who taken rescue medication by a given timepoint divided by the number of Participants treated in respective treatment group.

Participants with 'at least a 2-point PID':

Participants with observed PID score greater than or equal to 2 at any post dose timepoints will be considered as 'at least a 2-point PID'. The same previous formula will be used to calculate the Pain intensity difference (PID).

Participant's Global Assessment of Investigational Product:

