7.7.3 Summary of Efficacy Endpoint(s) Analysis Strategy

Endpoint	Statistical Method / Test	Analysis Populati on	Missing Data Imputation Approach	Parameters / Variables in the analysis (Stat. test/Model)	Analysis Time point
				treatment as main effect and baseline pain intensity (Numerical Rating Score) as the covariate	12-24, 16-24 and 0- 24 hours
Total pain relief from 0 to 2, 4, 6, 8, 12 and 24 hours post-dose	ANCOVA, Descriptive statistics	РР	No imputation and Single imputation	Same as Above	TOTPAR 0- 2, 0-4, 0-6, 6- 12, 0-8 0-12, 12-16, 16-20, 12-24, 16-24 and 0- 24 hours
Time to first use of rescue medication over 24 hours	Kaplan Meier Estimation Summary and graph	PP, ITT	No imputation	Statistical test: Median time will be compared between the treatment groups and placebo using a log-rank test stratified by baseline pain intensity (Categorical pain intensity), pair wise comparison will be made using Tukey- Kramer method (Rescue medication taken (Yes/No))	24 hours
Pain Intensity Difference (PID) and Pain Relief scores at 0.5, 1, 1.5, 2, 3, 4, 5, 6, 7, 8, 9, 10, 11, 12, 14, (16, 18, 20 if awake), 22 and 24 hours post- dose	Descriptive statistics, Graph	ITT	No imputation	Descriptive Statistics for PID derived from pain intensity score, Pain relief score	0.5, 1, 1.5, 2, 3, 4, 5, 6, 7, 8, 9, 10, 11, 12, 14, (16, 18, 20 if awake), 22 and 24 hours post-dose

Endpoint	Statistical Method / Test	Analysis Populati on	Missing Data Imputation Approach	Parameters / Variables in the analysis (Stat. test/Model)	Analysis Time point
Time to first perceptible relief measured by a stopwatch	Kaplan Meier Estimation Summary and graph	ITT	No imputation	Statistical test: Median time will be compared between the treatment groups and placebo using a log-rank test stratified by baseline pain intensity (Categorical pain intensity), pair wise comparison will be made using Tukey- Kramer method (Stopwatch 1)	24 hours
Time to meaningful relief measured by a stopwatch	Kaplan Meier Estimation Summary and graph	ITT	No imputation	Same as above model will be used. (Stopwatch 2)	At any timepoint after first perceptible pain relief measured in 24 hours
Time to first perceptible relief confirmed by meaningful relief	Kaplan Meier Estimation Summary and graph	ITT	No imputation	Same as above model will be used. (Stopwatch 1/ Stopwatch 2)	At any time for 24 hours

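### SAP 4.1 times meaningful relief from the second stopwatch only, so participants whose first relief was already meaningful, who never receive that watch, would be censored (secondary onset endpoint)

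*SAP*

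**What the plan says.** **Time to meaningful relief.** In SAP 4.1 the event occurs when someone "experiences relief that is meaningful after the administration of study drug and stops the second stopwatch. If it is not stopped, time will be censored"; the censoring time is the earlier of the last pain relief assessment and first rescue. SAP 3.1.1 allows no imputation of stopwatch data and sends missing values to that censoring rule. The row for this endpoint in the SAP 7.7.3 table names the second watch alone: "Same as above model will be used. (Stopwatch 2".

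**How the watches are used.** Protocol 8.1.6 has a branch that the SAP rule lacks. When stopwatch A is stopped, the participant is asked whether the relief is meaningful. After a Yes, the time for "meaningful pain relief confirmed will be the same time recorded as first perceptible pain relief", and "The participant will not be given the second stopwatch". Only after a No is stopwatch B handed over. Other passages omit the branch. Protocol 4.2 says that once the first watch is pressed "the participant is then given a second stopwatch and asked to depress the button when the relief is perceived as meaningful". Protocol 4.1 and SAP 2.2 say "The second stopwatch will be used to capture the time when pain relief becomes meaningful to the participant".

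**Perceptible relief confirmed by meaningful relief.** The Protocol synopsis, Protocol 3 and 9.4.1, and SAP 5.2 and 7.7.2 have this "defined as the time to perceptible pain relief (the first stopwatch time) for those participants who had meaningful pain relief (the second stopwatch time"). SAP 4.1 instead uses stopwatch A for those who confirmed at once and stopwatch B for the rest, and the 7.7.3 row names both watches. SAP 7.7.2 gives the first version and then refers to 4.1 for the definition. SAP 7.13 reports no changes from the protocol.

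**The concern.** A participant cannot stop a watch that was never handed over. Read literally, the SAP therefore treats people whose first relief was already meaningful as never having reached it. They also stay in the risk set until rescue or up to 24 hours, which lowers the estimated onset curve. If one arm has more immediate Yes answers, as a better or faster analgesic might, that arm loses more events. Onset by time to meaningful relief is a named secondary objective.

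The confirmed endpoint raises a separate problem. Two programmers working from the same SAP could produce different times for everyone who answered No and later stopped stopwatch B.

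**Working it through.** **1. The three onset rules side by side**

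| Participant | Protocol 8.1.6, meaningful relief | SAP 4.1, meaningful relief | SAP 4.1, confirmed endpoint | Synopsis, Protocol 3 and 9.4.1, SAP 5.2 and 7.7.2, confirmed endpoint |
|---|---|---|---|---|
| Yes at stopwatch A | A time, event | Censored | A time | A time |
| No at A, later stops B | B time, event | B time, event | B time | A time |
| Never meaningful | No event | Censored | Censored | Not an event |

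The SAP 4.1 rule for the confirmed endpoint matches Protocol 8.1.6 for meaningful relief row by row. The complete meaningful-relief curve would thus be produced, but under another endpoint's name. That holds only if the 4.1 version of the confirmed endpoint is programmed. If the SAP 5.2 version is used, no output contains the full time to meaningful relief.

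**2. Effect on the event rate**

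The documents give no planning figure for this endpoint, so there is none to reproduce. The only input taken from them is the arm size of 144 (Protocol 9.2, SAP 2.3). Let p be the true proportion reaching meaningful relief and s the share of these who answer Yes at stopwatch A. Both are assumptions.

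Crude event rate under the SAP rule = p x (1 - s)

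| p | s = 5% | s = 10% | s = 20% | s = 30% |
|---|---|---|---|---|
| 60% | 57% | 54% | 48% | 42% |
| 80% | 76% | 72% | 64% | 56% |
| 90% | 85.5% | 81% | 72% | 63% |

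At p = 80%, 144 x 0.80 = 115.2 events per arm. Events turned into censored times: 115.2 x 0.05 = 5.8 up to 115.2 x 0.30 = 34.6.

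**3. Effect on the comparison**

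The ratio of crude event rates, FDC to naproxen, is multiplied by (1 - s in the FDC arm)/(1 - s in the naproxen arm). Take assumed true rates of 80% and 70%, with s = 20% in the naproxen arm. The crude rates are equal when 0.80 x (1 - s in the FDC arm) = 0.70 x 0.80 = 0.56, that is, at s = 30% in the FDC arm. Beyond that the direction reverses. With s of 30% against 10%, the rates are 0.80 x 0.70 = 56% and 0.70 x 0.90 = 63%.

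**4. Illustration on the planned type of analysis**

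The SAP uses Kaplan-Meier and log-rank methods, so the effect was also simulated. In all runs, onset is 0.25 h plus an exponential time, those without meaningful relief rescue at 2 to 8 h, and Yes participants are censored at 24 h.

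- One arm, 75% reaching meaningful relief, exponential mean 1 h: the median is about 1.35 h when Yes participants count as events. Under the SAP rule it is 2.04 h at s = 20% and is not reached at s = 40%.
- Two arms of 144 with a true FDC benefit (80% against 70% reaching relief, onset rates 1.2 and 1.0 per hour), 2,000 replicates, unstratified log-rank: mean z is about +2.3 when Yes participants count as events. Under the SAP rule it is +1.3 with s = 30% in both arms, -1.2 at 40% against 20%, and -2.8 at 60% against 30%.

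The last two cases use FDC shares above the 5% to 30% range in step 2.

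**The case against.** The strongest reply is that no responder need be lost in practice. Protocol 8.1.6 records a meaningful-relief time on the CRF for Yes participants, SAP section 1 says the SAP is read with the protocol and CRF, and SAP 3.1.1 censors only missing stopwatch data. A programmer could use the recorded time. This makes the censoring conditional on a literal reading, but the 4.1 text and the 7.7.3 cell both point to that reading and nothing in the SAP directs otherwise.

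The SAP also follows protocol wording. Protocol 4.1 and 4.2 tie meaningful relief to the second watch, and only 8.1.6 has the Yes branch. This stands: for time to meaningful relief, the inconsistency starts in the protocol.

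The common wording of the confirmed endpoint is itself ambiguous, because its parenthesis ties meaningful relief to the second watch; read strictly, it could exclude Yes participants. That also stands. It does not remove the conflict for participants who answered No and later stopped stopwatch B: SAP 4.1 gives them the B time and the other passages the A time.

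Finally, every size rests on assumed p and s. The documents give no reason to expect a gap between arms large enough to reverse the comparison, and these endpoints lie outside the SPID0-8 testing sequence. All of this is correct and limits the weight of the point.

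**Conclusion.** The concern holds, and the definitions should be corrected. As written, SAP 4.1 censors participants who, under Protocol 8.1.6, have a recorded time of meaningful relief. The crude event rate falls by the factor (1 - s) in any arm with Yes answers. Attenuation is the likely result if shares are similar across arms; reversal needs a large enough gap between them. The numerical sizes depend on assumed p and s, and the simulated ones also on assumed onset and rescue times.

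The confirmed endpoint has two incompatible definitions, and for that endpoint the statement of no changes in SAP 7.13 is wrong. The damage is limited to secondary onset endpoints; no data are lost, and SPID0-8 and its sequence are untouched.

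**What to change.** Correct both definitions together in SAP 4.1, with the matching cells in 7.7.3:

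- **Time to meaningful relief:** stopwatch A time if the participant answered Yes at stopwatch A; otherwise stopwatch B time if B was stopped because relief became meaningful before any rescue; otherwise censored at the earlier of last pain relief assessment and first rescue.
- **Perceptible relief confirmed by meaningful relief:** stopwatch A time for everyone who reached meaningful relief by either route before rescue; all others censored by the same rule.
- **Watches stopped at rescue:** Protocol 6.5.1 has running watches stopped "at the time of rescue administration and recorded on the case report form". As a clarification, state that a time recorded for this reason alone is a censoring time, not an event.

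Then align the Protocol synopsis, Protocol 3, 4.1, 4.2 and 9.4.1, and SAP 2.2, 5.2 and 7.7.2 with Protocol 8.1.6. If the protocol is not amended, record the clarification in SAP 7.13. Settle this before unblinding, so that the choice of rule cannot depend on results.

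The cost is two definitions, two table cells and a phrase at each of eight places (five in the protocol, three in the SAP), or one note in SAP 7.13 in place of the five protocol edits. No new data are needed: Protocol 8.1.6 already records both times and the Yes/No answer, and 6.5.1 records the time of rescue.
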